### **14.1.3. Safety Measurements**

#### **14.1.3.1. Safety Profiling**

As is conventional, safety will be characterized in terms of the type, incidence, timing, severity, drug-relatedness, and seriousness of adverse events and laboratory abnormalities, and other safety assessments. For consistency of interpretation, adverse events will be coded using the MedDRA and the severity of these events and laboratory abnormalities will be graded using the well-defined CTCAE, Version 3.0. Version 3.0 will remain the reference for this study to facilitate comparison with safety data from previously conducted ataluren trials. Concomitant medications will be coded with the WHODRUG dictionary. ECG data will be evaluated in accordance with the relevant ICH ECG guidance.

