#### **11.4.6. Secondary Variables**

##### **11.4.6.1. 12-Lead ECG and Other Safety Parameters**

ECG and vital sign data will be listed and summarized by visit. Physical examination findings will be listed. Where appropriate, changes from baseline at each visit will be presented.

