4.11.2. Electrocardiographic Analyses

The assessments and change from baseline in electrocardiographic (ECG) parameters (e.g., RR, PR, QRS, QT, heart rate, QTcB, and QTcF) will be summarized by visit for the As-Treated population. Maximal and minimal change from baseline in each parameter will also be summarized.

Standard ECG intervals will be determined. The QT interval will be corrected by both the Bazett's and Fridericia's method as follows:

$$\text{Bazett's: } QTcB = QT / (RR)^{1/2}$$

$$\text{Fridericia: } QTcF = QT / (RR)^{1/3}$$

The QTc data obtained by using the Bazett and Fridericia corrections will be categorized separately into the following classifications and summarized by visit:

- QTc interval >450 msec and ≤480 msec
- QTc interval >480 msec and ≤500 msec
- QTc interval >500 msec

The change of the QTc values obtained by using the Bazett and Fridericia corrections will also be categorized separately as follows and summarized by visit:

- QTc interval increases from baseline by >30 msec and ≤60 msec
- QTc interval increases from baseline by >60 msec

QTc data will be presented in shift tables from baseline to each visit based on the categories: <450 msec, 450-480 msec, >480 msec.

The number and percentages of subjects with abnormal ECG parameter assessments will be tabulated by visit. Below list the abnormal criteria for the parameters:

- Heart rate > 140 bpm or < 50 bpm for age > 17 (or <60 for age 13-17, or <75 for age 6-12 and/or increase/decrease by > 30 bpm for heart rate;
- PR > 250 and/or increase by > 50 ms for PR interval;
- QRS > 120ms and/or increase by > 20 ms for QRS duration;
- QT, QTcB or QTcF > 500 ms and/or increase by > 60 ms for QT interval and its corrections.

Shift tables for the interpretation of the 12-lead ECG results (“normal”, “abnormal, clinically insignificant”, “abnormal, potentially clinically significant”) will be presented by treatment group to show the change in results from baseline (“normal”, “abnormal, clinically insignificant”, “abnormal, potentially clinically significant”) to each visit (“normal”, “abnormal, clinically insignificant”, “abnormal, potentially clinically significant”).

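### The SAP's ECG abnormality count includes rises in uncorrected QT and Bazett QTc, and its QTc shift table names no correction, so QT outlier counts mix heart-rate change with repolarisation change

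*Protocol*

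**What the plan says.** Change from baseline in 12-lead ECG measurements is part of a secondary endpoint (Protocol 3.2, SAP 2.3.2). Protocol 14.1.3.1 states in general terms that "ECG data will be evaluated in accordance with the relevant ICH ECG guidance". Protocol 11.4.6.1 asks for listings and by-visit summaries, adding that "Where appropriate, changes from baseline at each visit will be presented". It names no QT correction.

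SAP 4.11.2 supplies the detail:

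- **Parameters.** Values and changes are tabulated: "RR, PR, QRS, QT, heart rate, QTcB, and QTcF) will be summarized by visit for the As-Treated population". Maximal and minimal changes are added for each parameter.
- **Corrections.** "The QT interval will be corrected by both the Bazett's and Fridericia's method as follows". No lead measure is named.
- **Categories.** QTc values (>450, >480, >500 ms) and QTc increases (>30, >60 ms) "obtained by using the Bazett and Fridericia corrections will be categorized separately".
- **Shift table.** "QTc data will be presented in shift tables from baseline to each visit based on the categories", namely <450, 450-480 and >480 ms. The correction is not stated.
- **Abnormality count.** The QT criterion is "QT, QTcB or QTcF > 500 ms and/or increase by > 60 ms for QT interval and its corrections". The heart-rate criterion in the same list begins "Heart rate > 140 bpm or < 50 bpm for age > 17 (or <60 for age 13-17, or <75 for age 6-12" and also covers a change of more than 30 bpm in either direction.

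**The concern.** Uncorrected QT depends on heart rate, which is the reason for correcting it. A rule that counts a rise of more than 60 ms in uncorrected QT as abnormal therefore counts some changes that are purely heart rate. Bazett and Fridericia respond differently to rate, so the QTcB rows can also move when the QTcF rows do not. The plan does not say which measure carries the conclusion or how discordant results are to be read.

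In a randomised study, a control arm would show how many such flags arise without the drug. Here every subject receives ataluren. In addition, ECGs are scheduled at Screening but not at Week 1 (Protocol 8.2.9 and Table 3). Under SAP 5.1 the baseline is therefore normally one ECG, and its heart rate carries into every later change. What is at stake is the meaning of the QT outlier counts and of the shift table.

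**Working it through.** The documents give no ECG figure to reproduce. The check uses the two correction formulas in SAP 4.11.2.

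**Formulas.** With RR = 60/HR in seconds, QTcF = QT/RR^(1/3) and QTcB = QT/RR^(1/2). Hence QT = QTcF × RR^(1/3), and QTcB = QTcF × RR^(-1/6).

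**Input assumed.** QTcF is constant at 400 ms, meaning no repolarisation change by Fridericia. This is not in the documents.

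**Step 1: heart rate alone.** At 100 bpm, RR = 0.6, so QT = 400 × 0.6^(1/3) = 337.4 ms and QTcB = 400 × 0.6^(-1/6) = 435.5 ms. At 60 bpm, RR = 1, so both are 400 ms.

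| Heart rate (bpm) | QT change (ms) | QTcB change (ms) | QTcF change (ms) | QT-related result under SAP 4.11.2 |
|---|---|---|---|---|
| 100 to 60 | +62.6 | -35.5 | 0 | counted abnormal (QT >60) |
| 60 to 100 | -62.6 | +35.5 | 0 | QTcB in the >30 ms category |
| 90 to 75 | +21.9 | -12.8 | 0 | none |
| 75 to 60 | +28.7 | -15.2 | 0 | none |
| 75 to 50 | +53.7 | -27.1 | 0 | none |

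For QTcF of 380 and 420 ms, the 100 to 60 bpm change gives QT +59.5 and +65.8 ms, so this example lies close to the threshold.

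**Step 2: how large a fall is needed.** At QTcF 400 ms, QT crosses +60 ms at 61 bpm from 100, 56 from 90, 51 from 80 and 48 from 75. The >500 ms limb needs RR = (500/400)^3 = 1.953 s, a heart rate of about 31 bpm, so heart rate alone hardly ever reaches it.

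**Step 3: offsetting.** If QTcF truly rises by 35 ms while heart rate falls from 100 to 60 bpm, QTcB changes by 435 - 435.5 = -0.5 ms. With a true rise of 65 ms, QTcB changes by 465 - 435.5 = +29.5 ms, just short of the >30 ms category. The QTcF rows show +35 and +65 ms.

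**Step 4: illustrative frequency.** A simulation took 70 subjects with 13 post-baseline ECGs, no true QTcF change and no heart-rate trend. It assumed mean heart rate 85 bpm (between-subject SD 10, within-subject SD 6 to 10) and mean QTcF 405 ms (between-subject SD 15, within-subject SD 8 to 12). None of these values is in the documents. The mean number of subjects with a >60 ms rise at any visit was:

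- QT, QTcB or QTcF, as in the SAP: 0.3 to 9.7 of 70
- uncorrected QT alone: 0.3 to 8.0
- QTcB alone: 0.0 to 1.9
- QTcF alone: 0.0 to 0.2

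Most of the excess comes from uncorrected QT. The roughly 30-fold range shows how far the count depends on the assumptions.

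**The case against.** **A QTcF signal is not lost.** A reader might infer from Step 3 that the plan can hide a real increase. It does not. QTcF has its own by-visit changes and its own categories, and an either/or rule cannot cancel a QTcF flag. Offsetting is confined to the QT and QTcB rows and, if Bazett is used, to the shift table.

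**Heart rate is reported and flagged alongside.** This largely stands. At constant QTcF 400 ms, the crossings from 100 and 90 bpm are falls of about 39 and 34 bpm, beyond the 30 bpm limit, and the crossing from 75 ends below 50 bpm. Only a narrow band of adult starting rates near 80 bpm escapes. With ordinary QTcF variation a smaller fall can suffice, so some QT flags would come without a heart-rate flag. No rule tells the reader to discount those that come with one.

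**Growth.** A reader might take the 75, 60 and 50 bpm limits as evidence of a built-in trend in minors. They are abnormality cut-offs, not expected means. Moving between them gives at most +53.7 ms. SAP 2.1 also states that the study ends early, with ongoing subjects discontinued, which shortens the time for age-related slowing.

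**Fridericia is treated as the truth.** This is fair: neither document shows that it is the right correction in this population. If QTcB is held at 400 ms instead, 100 to 60 bpm moves QTcF by about +33 ms. Uncorrected QT then goes from 400 × 0.6^(1/2) = 309.8 to 400 ms, a rise of 90.2 ms. The objection therefore bears on the choice of lead measure and leaves the case against flagging uncorrected QT intact.

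**Guidance.** A reader might infer a breach of the ECG guidance cited in Protocol 14.1.3.1. That guidance is not in the documents, so the point cannot be judged and is not relied on.

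**Low consequence.** SAP 4.2 calls all analyses descriptive. No test, stopping threshold or primary endpoint uses these tables. This stands.

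**Conclusion.** The concern holds in a limited form. As written, SAP 4.11.2 counts some heart-rate changes as QT abnormalities, and it leaves the correction in the QTc shift table open. The direction follows from the SAP's formulas. The +62.6 and -35.5 ms figures rest on the assumed QTcF of 400 ms and a 40 bpm change. The number of subjects affected cannot be stated from the documents, because they give no heart-rate or QTc variability.

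The documents do not support saying that a true QTcF increase is masked, that the plan builds in an age trend of known size, or that it departs from the cited guidance. The effect is limited to reading the QT and QTcB outlier counts and the shift table, for a descriptive secondary safety endpoint in a single-arm study. This is a minor but worthwhile correction.

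**What to change.** Amend SAP 4.11.2 before database lock, as SAP section 1 allows:

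1. Designate one rate-corrected measure, QTcF, for the QTc shift table and for the >500/>60 ms abnormality count.
2. Remove uncorrected QT from the >60 ms criterion. Basing the count on QTcF also takes it out of the >500 ms limb, which makes almost no practical difference.
3. Keep QT, QTcB and heart rate as supportive descriptive output without a QT abnormality flag.

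The cost is SAP wording and minor table programming. No new data are needed. The small downside is that the lead result then rests on one correction formula, so QTcB should stay visible for comparison.

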#### **14.1.3.2. Study Drug Compliance**

Evaluation of study drug compliance provides context for assessments of pharmacological activity, safety, and PK, and may offer a general indication of subject acceptance of therapy, integrating factors of tolerability, palatability, and convenience. The compliance of the subject will be verified by counting used ataluren sachets.

#### **14.1.4. Required Laboratory Values**

The required laboratory values for eligibility are necessary in order to implement the safety monitoring plan described in [Section 6.3](#).

Minimal reversible serum transaminase elevations (ALT, AST) have been observed in healthy volunteers receiving ataluren ([Section 2.2.3.1](#)) [[Hirawat 2007](#)]. However, because such findings have not been prominent in prior nmCF clinical trials testing ([Section 2.2.3](#)), and because many patients with CF may have chronic elevations in serum ALT, AST, and GGT, it is not practical to exclude all patients with such abnormalities. Therefore, candidates with Grade 1 elevations in serum ALT, AST, or GGT values at screening may be enrolled. Patients with more severe elevations in these parameters or with chronic active hepatitis infections will be excluded. The requirement that subjects have a screening serum albumin  $\geq 3.0$  g/dL (in conjunction with exclusion for those with known portal hypertension) avoids accrual of those who have profoundly unstable hepatic or nutritional status.

Mild nephrosis in mice has been observed in toxicology studies. Renal findings in Study 009 included episodes of creatinine elevations and nephrolithiasis. Overall, treatment-emergent renal adverse events were seen more frequently in the ataluren arm; cases of reversible Grade 3-4 creatinine elevations were observed in the ataluren arm, which were associated with the treatment of exacerbations with nephrotoxic systemic antibiotics and, in some cases, dehydration. Non-serious episodes of creatinine elevation occurred predominantly in the ataluren arm and were transient, generally mild, and resolved with or without interruption of study medication. However, there was no clinically meaningful difference in creatinine between the ataluren and placebo arms at Week 48, indicating that there was no cumulative effect of these transient elevations on renal function. The incidence of new onset nephrolithiasis was similar in both arms (5 patients [4.2%] on ataluren vs 4 patients [3.4%] on placebo).

Thus, ultrasound will be performed in each subject during screening to establish an anatomic baseline against which to compare any future renal findings and subjects must have adequate baseline renal function as established by serum markers (cystatin C, creatinine, BUN), urine

markers (protein and blood), and serum electrolytes (Na+, K+, HCO3, Mg2+, Ca2+, and phosphate).

During the Phase 2b double-blind study of ataluren in nmDMD (PTC124-GD-007-DMD), mean total cholesterol and triglycerides were in the upper range of normal at baseline and increased on study, reaching borderline high or high values. Baseline mean cholesterol and triglycerides values were higher in patients receiving systemic corticosteroid therapy. During the treatment period, increases in mean cholesterol levels were observed in patients receiving systemic corticosteroid therapy, more prominently in ataluren-treated patients than in the placebo arm. In patients not receiving systemic corticosteroid therapy, mean cholesterol levels increased similarly across all 3 treatment arms (placebo, 10-, 10-, 20-mg/kg TID, and 20-, 20-, 40-mg/kg TID), and mean triglyceride levels increased minimally in ataluren-treated patients. Similar changes were not seen in the double-blind study for nmCF (Study 009). In that study, low cholesterol levels were observed prior to treatment in >40% of patients across both treatment arms. No ataluren-treated patients shifted from normal cholesterol at baseline to high cholesterol at Week 48. Shifts from normal triglycerides at baseline to high triglycerides at Week 48 were observed in both treatment arms, and were somewhat higher in placebo. Despite the lack of effect of ataluren on total cholesterol and triglycerides in nmCF, total cholesterol and triglycerides will continue to be monitored throughout this study.

#### **14.1.5. Reproductive Considerations**

Ataluren is not genotoxic, did not affect fertility in male and female rats, and was not teratogenic in rats and rabbits. In addition, lack of sexual maturity in many of the patients likely to be enrolled in this study limits reproductive risks. However, restriction on eligibility relating to willingness to avoid unprotected sexual intercourse in any patients known to be sexually active is included as a general precaution.

#### **14.1.6. Prior and Concomitant Therapies**

Conventional supportive therapies will be permitted; however, efforts will be made to avoid use of concomitant medications that might confound interpretation of study results or pose a safety risk. Ataluren has not proved allergenic in studies performed to date, but review of known allergies to excipients containing in the formulation is prudent. Concomitant use of potentially nephrotoxic antibiotics (eg, aminoglycosides and vancomycin) with ataluren is prohibited.

Aminoglycosides, eg, tobramycin, are theorized to ribosomally interfere with ataluren's mechanism of action. In previous Phase 3 studies of ataluren, notable differences in treatment effect have been observed in ataluren-treated patients that had been concomitantly treated with chronic inhaled aminoglycosides (eg, tobramycin) vs patients that were not administered chronic inhaled aminoglycosides (eg, tobramycin), which have a ribosomal-binding mechanism of action. An in vitro experiment confirmed this ribosomal mechanistic interference theory [Study Report PTC124-12030]. For these reasons, inhaled aminoglycoside use cannot occur within four months prior to the Screening Visit, and it is strongly recommended that alternative agents be utilized for CF treatment/prophylaxis.

In vitro studies have suggested that ataluren is potentially an inhibitor of cytochrome P450 (CYP) 2C8 and 2C9 at concentrations that may be achieved in the clinic. Because ataluren may slow the clearance of medications that are primarily metabolized by CYP2C8 or CYP2C9,

investigators should pay specific attention to use of drugs that are known substrates of this enzyme, particularly when such drugs may have a low therapeutic index.

While no clinical evidence of drug-drug interactions has been demonstrated, the potential for ataluren interactions with other drugs has been assessed. Based on in vitro studies, ataluren is a substrate of UGT1A9 and breast cancer resistant protein (BCRP). Caution should be exercised when ataluren is co-administered with drugs that are inducers of UGT1A9 (eg, phenobarbital, rifampin), or inhibitors of BCRP (eg, cyclosporine, eltrombopag, gefitinib).

In vitro data indicate that ataluren is an inhibitor of UGT1A9, organic anion transporter 1 (OAT1), organic anion transporter 3 (OAT3) and organic anion transporting polypeptide 1B3 (OATP1B3). Caution should be exercised when ataluren is co-administered with drugs that are substrates of UGT1A9 (eg, propofol, mycophenolate mofetil), OAT1, OAT3, or OATP1B3 (eg, oseltamivir, acyclovir, ciprofloxacin, captopril, furosemide, bumetanide, valsartan, pravastatin, rosuvastatin, atorvastatin, pitavastatin) because of the risk of increased concentration of these drugs.

Physicians and subjects are encouraged to avoid the use of extraneous drugs or alternative therapies in order to minimize the possibility that drug-drug interactions might occur. In particular, physicians are advised to closely monitor subjects when drugs of low therapeutic index that are cleared by CYP2C9 (eg, phenytoin or warfarin) are administered concomitantly with ataluren.

## **14.2. Treatment Rationale**

### **14.2.1. Schedule and Ataluren Dose Selection**

Dosing based on body weight will continue to be employed. Such dosing reduces variability in exposure by accommodating differences in subject size across the span of ages in subjects who will participate in the clinical study program.

The schedule of drug administration is derived directly from Phase 1 PK modeling and from Phase 2 exposure information. The intent of administering two smaller doses at 6-hour intervals during the day and a larger dose at a 12-hour interval overnight (eg, at 7:00 AM, 1:00 PM, and 7:00 PM) is to optimally sustain target plasma concentrations while minimizing total exposures. This schedule is likely to fit well with daily patterns of living for subjects, thus enhancing compliance.

### **14.2.2. Duration of Therapy**

Duration of therapy in this study is intended to provide approximately 4 years of additional safety data for nmCF patients that have completed Study 009, and as a secondary outcome, to provide additional long-term efficacy data in this population. Study duration may be expanded to include multiple years, if so determined by PTC Therapeutics.

### **14.2.3. Safety Monitoring**

In response to the occurrence of renal toxicology findings in the mouse and renal laboratory abnormalities in prior ataluren studies, the renal safety monitoring plan utilized for the previous Phase 3 study is also appropriate for renal monitoring of this study population. Thresholds for evaluation and intervention have been established for other types of adverse events or laboratory abnormalities observed in the study, including hepatic abnormalities. The intent is to protect subjects, obtain a thorough assessment of any clinically relevant adverse events or laboratory

abnormalities, and to offer recommendations for interruption and dose modification of ataluren in response to potential safety signals. The nature of these risks and the measures to monitor for them will be reflected in the informed consent form.

As noted in [Section 6.3](#), subjects must be monitored closely for adverse events or laboratory abnormalities during the course of the study. [Section 6.3](#) provides information on actions to be taken in the event that abnormalities are noted on specified monitoring studies. Thresholds are provided for interrupting ataluren immediately, for interrupting ataluren after confirmation of a value beyond the threshold, or for continuing ataluren while evaluating for potential drug-related toxicity.

#### **14.2.3.1. Renal Abnormalities**

##### **14.2.3.1.1. Overview**

Renal findings were seen in mice receiving one or two doses through 26 weeks of dosing with ataluren (A no-observed-adverse-effect level [NOAEL] for the renal toxicity findings in mice has not been identified; the lowest observed adverse effect level [LOAEL] = 75 mg/kg/day). Exposure in mice at 75 mg/kg/day is 0.3-fold the exposure in patients administered ataluren at the morning, midday, and evening doses of 10-, 10- and 20-mg/kg/day, respectively. The renal finding was seen primarily in the distal nephron and involved some degenerative changes (apoptosis) and regenerative changes (proliferation of renal epithelium) accompanied by tubular dilatation and proteinaceous material within the tubules. Rarely the tubules were mineralized. Fibrosis was not seen after 1 month of dosing, but an interstitial renal fibrosis was observed in the 26-week carcinogenicity study in mice. The finding was occasionally accompanied by individual increases in serum blood urea nitrogen (BUN) and/or creatinine, but a dose relationship for these parameters was not observed. The kidney findings were partially to completely reversible as soon as 2 to 6 weeks after cessation of dosing. The renal toxicity was observed in mice only, and has not been seen in rats dosed for 24 months or in dogs dosed for 52 weeks despite achievement of exposures in rats and dogs that were comparable to or greater than those observed in mice.

In Phase 1 studies in healthy volunteers and Phase 2 studies in patients with DMD and cystic fibrosis, renal laboratory abnormalities have been infrequent.

In the Phase 3 clinical trial (Study 009), serious adverse events related to renal dysfunction, which occurred only in the ataluren arm, included 3 patients with acute renal failure, 3 patients with renal failure, and 1 patient with hypercreatininemia. These events were characterized by elevated creatinine (Grade 1 to Grade 4), which resolved over days to weeks. Only 1 patient experienced symptoms of renal dysfunction (transient oliguria). All 7 events were associated with concomitant systemic treatment with potentially nephrotoxic antibiotics (eg, aminoglycosides, vancomycin) that were generally administered as treatment for pulmonary exacerbations. No patient required dialysis. One patient was unblinded and 1 patient chose not to continue study drug treatment; the remaining 5 of 7 patients restarted study medication and continued study participation without recurrent creatinine elevations. This issue was recognized during the conduct of the study and changes were made in the protocol (eg, prohibition of concomitant use of potentially nephrotoxic agents), which successfully addressed the issue. Non-serious creatinine elevations occurred predominantly in the ataluren arm and were transient, generally mild, and resolved with or without interruption of study medication. The incidence of treatment emergent nephrolithiasis was similar in the ataluren and placebo groups.

The renal monitoring program included in this protocol considers nonclinical and clinical findings with ataluren, and past experience with known nephrotoxins. Concomitant use of potentially nephrotoxic antibiotics with ataluren is prohibited. A focus is placed on well-established clinical indicators of renal dysfunction for making diagnostic decisions and prompting treatment interruptions/modifications in individual patients. The rationale for each of the decision-making parameters is discussed below.

